2.3.3 Risk Assessment

Dapagliflozin administration is well tolerated with a well-established safety profile. The potential and identified risks of dapagliflozin treatment have been well characterised through the dapagliflozin clinical development program and from post-marketing data. In clinical studies, commonly reported AEs include UTIs, genital infections, polyuria, and hypoglycaemia when combined with insulin or a sulfonylurea. In addition, DKA was commonly seen in clinical trials in patients with T1DM treated with dapagliflozin but was rare in clinical trials in patients with T2DM. See [Table 2](#) for further details.

The adverse clinical effects of zibotentan observed in healthy volunteers and oncology populations were largely due to its pharmacologically-mediated effects on ET_A receptor antagonism resulting in vasodilation, which are headache, hypotension, nasal congestion, peripheral oedema, conjunctival reddening, dizziness, flushing, minor decreases in systemic vascular resistance, minor increases in cardiac output, and effects due to haemodilution which lead to a reduction in Hb concentration, haematocrit and anaemia. Reduction in Hb tends to develop within a month of commencing the drug and is mild in most patients (CTC Grade 1/2), nonprogressive and tends to reverse on stopping the drug. However, some patients in oncology studies have developed clinical anaemia. The adverse clinical effect of heart failure has been observed, being more commonly reported in CRPC patients receiving zibotentan than in those receiving placebo. The frequency of reports in patients receiving zibotentan has been less than 10% and most cases have responded to standard heart failure treatment. See [Table 2](#) for further details.

More detailed information about the known and potential benefits and risks of zibotentan and dapagliflozin may be found in respective Investigator's Brochures ([Zibotentan Investigator's Brochure](#) including the FDC development, and [Dapagliflozin Investigator's Brochure](#)).

Table 2 Risk Assessment

Potential risk of clinical significance	Summary of data/rationale for risk	Mitigation strategy
Dapagliflozin		

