4.2 Scientific Rationale for Study Design

The mechanisms of action of zibotentan and dapagliflozin are different and the outcome of combined treatment is expected to be complementary. Fluid retention is a class effect of endothelin receptor antagonists which may limit their potential use as monotherapy in cirrhosis. It is anticipated that potential fluid retention risk from zibotentan will be mitigated by the osmotic diuretic effects of dapagliflozin without increasing the risk for hypo- or hyperkalaemia, hyponatraemia, or hypovolaemia. By investigating the effects of zibotentan monotherapy as compared to the combination of zibotentan and dapagliflozin and placebo the importance of dapagliflozin to reduce the risk for fluid retention caused by zibotentan will be evaluated. A placebo arm is included to assess the effect of zibotentan monotherapy.

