9.4.3.3 Laboratory Assessments

Laboratory parameters will be presented for each treatment group.

For each scheduled post-baseline visit, descriptive statistics for all clinical chemistry, electrolyte, coagulation, and haematology parameters will be presented for observed values and change from baseline.

Elevation in liver parameters for assessment of Hy's law (see Appendix E) will be done and reported appropriately if potential cases have been identified during the course of the study.

Key participant information will be presented for participants with treatment-emergent changes in laboratory parameters outside of predefined criteria.

Supportive laboratory listings will cover observed values and changes from baseline for each individual participant as well as abnormalities.

Details of laboratory analyses including definition of abnormality criteria (eg, definition of low, normal, high) and study-specific predefined criteria for treatment-emergent changes in relevant laboratory parameters will be provided in the SAP.

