4.6.3 Clinical Laboratory, Blood Sample

4.6.3.1 Definitions and Derivations

Blood samples for determination of clinical laboratory assessments are collected according to the CSP. Clinical laboratory assessments of blood samples, including electrolytes, will be categorised into haematology, chemistry and coagulation parameters as defined below in [Table 9](#).

Table 9 Clinical blood laboratory parameters

Haematology	
White blood cell count	Lymphocytes absolute count
Red blood cell count	Monocytes absolute count
Haemoglobin	Eosinophils absolute count
Haematocrit	Basophils absolute count
Neutrophils absolute count	Platelet absolute count
Chemistry	
BUN	Alanine aminotransferase
Creatinine and calculated eGFR (CKD-EPI) and eGFR2	Aspartate aminotransferase
Total bilirubin and direct bilirubin	Alkaline phosphatase
Albumin	Creatine kinase
Calcium	Serum glucose
Phosphate	Gamma-glutamyl transferase
Serum Osmolality	NT-pro BNP
Bicarbonate (HCO ₃ ⁻)	Sodium
Chloride (Cl ⁻)	Potassium
Magnesium (Mg ⁺)	
Coagulation	
International normalised ratio	Prothrombin time
Partial thromboplastin time	

Assessed values of the form ‘<x’ (below the lower limit of quantification) or ‘>x’ (above the upper limit of quantification) will be imputed as ‘x’ in calculation of summary statistics but displayed as ‘<x’ or ‘>x’ in listings.

Treatment emergent

A treatment emergent abnormality is defined as either of below:

- A switch in parameter from normal at baseline to abnormal at post-baseline accordingly to predefined criteria, see below for predefined criteria.
- A baseline value that met the criteria for abnormality and the post-baseline value is more extreme (further from the limit), see below for predefined criteria.

When the predefined criteria for a parameter abnormality is referring to ULN then this is based on reference ranges from the central laboratory. For some parameters there are different criteria for the same parameter that can be separately fulfilled and will be presented separately.

Predefined criteria for Haematology

Platelet absolute count ($10^9/L$): <50, <75

Predefined criteria for Chemistry

NT-pro BNP (pg/mL): >1 x 125, >2 x 125, >5 x 125

Alanine aminotransferase (U/L), Alkaline phosphatase (U/L), Aspartate aminotransferase (U/L): >1 x ULN, >3x ULN, >5 x ULN

Direct bilirubin (mg/dL): >1 x ULN, >2x ULN, >3x ULN

Total bilirubin (mg/dL): >1 x ULN, >2x ULN, >5 x ULN

Alkaline phosphatase (U/L): ≥ 2 x baseline

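### The SAP sets no treatment-emergent criterion or shift category for haemoglobin, sodium or potassium, so no planned laboratory table counts by arm the participants who cross a limit

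*SAP*

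**What the plan says.** Protocol 2.3.3 lists among the observed effects of zibotentan "effects due to haemodilution which lead to a reduction in Hb concentration, haematocrit and anaemia". It describes the haemoglobin fall as usually mild, non-progressive and reversible, and tending to appear within a month of starting. It then adds: "However, some patients in oncology studies have developed clinical anaemia". Protocol 4.2 expects dapagliflozin to offset fluid retention "without increasing the risk for hypo- or hyperkalaemia, hyponatraemia, or hypovolaemia".

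Protocol 9.4.3.3 assigns the definitions to the SAP, which is to set what counts as low, normal or high: "study-specific predefined criteria for treatment-emergent changes in relevant laboratory parameters will be provided in the SAP". The same section ties individual reporting to those criteria: "Key participant information will be presented for participants with treatment-emergent changes in laboratory parameters outside of predefined criteria".

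SAP 4.6.3.1 covers electrolytes in its scope: "Clinical laboratory assessments of blood samples, including electrolytes, will be categorised into haematology, chemistry and coagulation parameters". Haemoglobin, sodium and potassium are all in its Table 9. The first route to a treatment-emergent abnormality is "A switch in parameter from normal at baseline to abnormal at post-baseline accordingly to predefined criteria, see below for predefined criteria"; the second is an already abnormal baseline value that becomes more extreme under the same criteria. Under "Predefined criteria for Haematology" there is only platelet count. Chemistry has NT-proBNP, ALT, AST, ALP, and direct and total bilirubin, plus a combined transaminase and bilirubin criterion. Coagulation has INR. The shift tables use the same parameters without INR, which has its own table of maximum value against baseline (SAP 4.6.3.2). These lists carry no redaction mark.

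**The concern.** This is a safety study, and its protocol singles out one laboratory effect of the investigational drug and states an expectation about two electrolytes. The natural safety question for each is how many participants per arm went below or above a limit at any point on study. The SAP answers that question for platelets and liver tests but not for haemoglobin, sodium or potassium. The laboratory key subject information uses the same criteria, so a marked fall or rise in one of these three would not by itself bring a participant forward for individual presentation. SAP section 2, which records departures from the protocol, does not say that these parameters were judged not relevant.

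**Working it through.** The plan states no figure to reproduce. The check sets the parameter list against the criteria, and then asks what the other planned displays show.

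**1. Coverage.** Inputs: SAP Table 9, with combined entries split (total and direct bilirubin; creatinine, eGFR and eGFR2), and the criteria and shift lists in SAP 4.6.3.1.

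| Group | Parameters | With an emergent criterion | In a shift table |
|---|---|---|---|
| Haematology | 10 | 1 (platelets) | 1 |
| Chemistry | 22 | 6 (NT-proBNP, ALT, AST, ALP, direct and total bilirubin) | 6 |
| Coagulation | 3 | 1 (INR) | 0 |
| Total | 10 + 22 + 3 = 35 | 1 + 6 + 1 = 8 | 1 + 6 + 0 = 7 |

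Of the five electrolytes within chemistry (bicarbonate, chloride, magnesium, sodium, potassium), 0 have a criterion. For haemoglobin, sodium and potassium the count is 0 of 3 in both columns.

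**2. Consequence of the definition.** Both routes to a treatment-emergent abnormality need a predefined criterion. A parameter without one cannot be treatment-emergent, so it cannot enter the emergent table or trigger the key subject information for laboratory abnormalities in SAP 4.6.3.2.

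**3. What remains planned for the three parameters.**
- By-visit descriptive statistics for observed values and change from baseline (SAP 4.6.3.2). SAP 3.3 defines these to include minimum and maximum.
- Participant listings that flag values outside laboratory reference ranges (SAP 4.6.3.2).
- Adverse event tables by arm (SAP 4.6.2.2), where a laboratory change meets Protocol 8.4.4: serious, the reason for stopping study drug, or clinically relevant in the investigator's judgement.

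**4. Whether these replace the missing count.** A by-visit minimum is one value per arm and visit. It does not say whether one participant or several crossed a limit, or whether the extremes at different visits belong to the same person. SAP 3.3.2 also keeps one value per window, the one nearest the target day. For Week 3 the window is Day 19 to Day 31 with target Day 22. If the scheduled sample falls on Day 22, an extra sample taken from Day 23 to Day 31 because of a clinical concern (allowed by Protocol 8.3.5) does not enter the by-visit table. SAP 3.3.2 does keep all observations for participant-level extremes. The emergent and shift tables are of that kind, but these three parameters are not in them. Listings flag the values without comparing arms, and adverse event reporting is selective by design.

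**The case against.** The strongest reply is that the information is largely there. A participant with a large haemoglobin fall at a scheduled visit would appear as that arm's minimum change, would be flagged in the listing, and might be reported as anaemia; Protocol 8.4.4 uses that very example. A serious case, or one that ended treatment, would reach key subject information through the adverse event route. The AESI categories are largely redacted, so overlap with these parameters cannot be excluded. This stands, and it limits the gap to a systematic count by arm.

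A second reply is that the protocol promises emergent criteria only for relevant parameters. The visible risk rows in Protocol Table 2 are ketoacidosis, fluid retention, heart failure, hypotension and teratogenicity, and Protocol 2.3.5 names hypotension, fluid retention and heart failure. Platelets, liver tests, INR and NT-proBNP are a coherent choice for that list. This carries some weight for sodium and potassium, which the protocol mentions as risks not expected to rise. It carries less for haemoglobin, which Protocol 2.3.3 reports as an observed drug effect likely to appear within the six-week treatment period.

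A third reply is that plain reference limits would misfire. The SAP counts any worsening of an already abnormal baseline as emergent, and no entry limit for these three parameters is visible in Protocol 5.1 or 5.2. A trivial further fall would then be flagged. This is correct and shapes the fix.

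A reader might go further and infer that the trial cannot speak to the electrolyte expectation at all. The documents do not support that. The expectation is an anticipation in the rationale, no objective tests it beyond general safety laboratory tests, and the displays above do bear on it. Nor would the added counts settle it: with 0 events among 22 participants, the one-sided 95% upper limit is 1 − 0.05^(1/22) = 12.7%.

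**Conclusion.** The omission is real and is visible in unredacted text: none of haemoglobin, sodium and potassium has an emergent criterion or shift category, against 8 and 7 of 35 parameters that do. The consequence is specific. No planned laboratory table counts, by arm, the participants who cross a limit at any time, and these parameters cannot trigger the laboratory key subject information. The case is strongest for haemoglobin. It rests on reading the lists in SAP 4.6.3.1 as complete and on treating a drug effect named in the protocol as relevant under Protocol 9.4.3.3.

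Two stronger readings do not hold. It is not the case that the emergent table would report a misleading zero for haemoglobin: it would have no haemoglobin row. Nor do the documents give the same grounds for adding creatinine: eGFR already has its own repeated-measures analysis and by-visit summary (SAP 4.2.10), and a partly redacted AESI definition in Protocol 8.4.6 appears to address acute renal change.

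This is a cheap improvement to safety reporting. It does not affect the key endpoints.

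**What to change.** Before data lock, amend SAP 4.6.3.1 and 4.6.3.2 as follows.

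- Add shift rows from baseline to minimum for haemoglobin, and from baseline to minimum and to maximum for sodium and potassium, using all on-study observations, unscheduled samples included.
- Add treatment-emergent counts by arm for the same parameters. Use graded or change-from-baseline cut-offs chosen by the sponsor, not the plain reference limit alone, so that slight worsening of an already abnormal baseline is not counted.
- Let these criteria trigger the laboratory key subject information.
- If the sponsor prefers to leave a parameter out, state in the SAP why it is not relevant under Protocol 9.4.3.3.

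No new data are needed. The cost is choosing the cut-offs, a few extra rows in tables of a kind already planned, and a slightly longer safety section.

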Alanine aminotransferase (U/L), Aspartate aminotransferase (U/L): ≥ 2 x baseline and > 1 x ULN

Direct bilirubin (mg/dL): ≥ 1 mg/dL over baseline

Total bilirubin (mg/dL): ≥ 2 x baseline and > 2 x ULN

Combination criteria: Aspartate aminotransferase (U/L) or Alanine aminotransferase (U/L) ≥ 3 x ULN and Total bilirubin (mg/dL) > 2 x ULN

Predefined criteria for Coagulation

INR: $> 0.2 +$ Baseline, $> 0.4 +$ Baseline, $> 0.6 +$ Baseline

Shift table definitions

Below parameters will be categorised according to below categories for the shift tables.

Haematology, shift from baseline to minimum value

Platelets ($10^9/L$) with categories: <50, ≥ 50 - < 75 , ≥ 75 - < 150 , ≥ 150 - < 400 , ≥ 400

Chemistry, shift from baseline to maximum value

Alanine aminotransferase (U/L), Alkaline phosphatase (U/L), Aspartate aminotransferase (U/L), Direct bilirubin (mg/dL), Total bilirubin (mg/dL) with categories: Normal(\leq ULN), High ($> 1 \times$ ULN and $\leq 2 \times$ ULN), Higher ($> 2 \times$ ULN and $\leq 5 \times$ ULN), Highest ($> 5 \times$ ULN). N-Terminal proB-type natriuretic peptide (pg/mL) with categories: Normal($\leq 1 \times 125$), High ($> 1 \times 125$ and $\leq 2 \times 125$), Higher ($> 2 \times$ ULN and $\leq 5 \times 125$), Highest ($> 5 \times 125$).

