4.6.3.2 Presentations

All laboratory data will be presented in SI or conventional units.

The haematology, chemistry and coagulation parameters defined in [Table 9](#) will be presented as continuous variables using descriptive statistics as specified in section [3.3](#) and will be presented by treatment group and by scheduled post-baseline visits for observed values and change from baseline.

The number of subjects with treatment-emergent laboratory parameter abnormalities will be presented categorically by treatment group. Only the most extreme value per subject will be accounted for.

Shift tables from baseline to maximum or minimum value will also be presented by treatment group. For INR summary table for maximum on study value as compared to baseline will be presented.

Scatter plot of maximum ALT or AST versus maximum total bilirubin and corresponding tabulation will be presented as well.

Key subject information will be presented for subjects with treatment emergent abnormalities for haematology, chemistry or coagulation abnormalities.

Additional key subject information and graphs of individual data will be presented including laboratory parameters which are associated with liver safety. This will be done for e.g. subjects with investigational product interruptions and discontinuations, subjects with DILI/modified Hy's Law.

Supportive laboratory listings will cover observed values and changes from baseline for each individual participant as well as abnormalities as compared to laboratory reference ranges.

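### The NT-proBNP shift category Higher starts at 2 x ULN although every other bound is a multiple of 125 pg/mL, so unless the ULN is exactly 125 some values belong to no category or to two

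*SAP*

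**What the plan says.** SAP section 4.6.3.1, under the shift table definitions for chemistry (shift from baseline to maximum value), lists "N-Terminal proB-type natriuretic peptide (pg/mL) with categories" as follows:

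- Normal: up to 1 x 125 pg/mL.
- High: above 1 x 125 and up to 2 x 125.
- Higher: written as "Higher ($> 2 \times$ ULN and $\leq 5 \times 125", that is, above 2 x ULN and up to 5 x 125.
- Highest: above 5 x 125.

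The treatment-emergent criteria earlier in the same section are "NT-pro BNP (pg/mL): >1 x 125, >2 x 125, >5 x 125", with no ULN.

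On the meaning of ULN, the section says of the predefined abnormality criteria that a criterion "referring to ULN then this is based on reference ranges from the central laboratory". Neither the SAP nor the protocol states a ULN for NT-proBNP.

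Section 4.6.3.2 makes the categories operative: "Shift tables from baseline to maximum or minimum value will also be presented by treatment group".

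**The concern.** A shift table needs categories that cover every value once. Here one bound depends on a laboratory limit that the documents do not give, and the bounds around it are fixed numbers. A programmer who follows the text literally may find values with no category, or values with two, and would have to settle the matter without a documented rule. The problem applies to the baseline value as well as the maximum, so both the rows and the columns of the table are exposed.

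Fluid retention and heart failure are among the zibotentan risks listed in the protocol's risk assessment (section 2.3.3), and NT-proBNP is a safety laboratory test at every visit in the schedule of activities. With about 22 participants per arm, one participant placed in the wrong cell, or in none, moves a percentage by about 1/22 = 4.5 points. The shift table and the treatment-emergent table would also use different cut-points for what reads as the same threshold, so they might not reconcile.

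**Working it through.** **Inputs.** The category bounds and the treatment-emergent thresholds come from SAP 4.6.3.1. The ULN, written U below, is in neither document, so the values used here are assumptions that show the range.

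**Bounds in pg/mL.** 1 x 125 = 125; 2 x 125 = 250; 5 x 125 = 625. As written:

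- Normal: x ≤ 125
- High: 125 < x ≤ 250
- Higher: 2U < x ≤ 625
- Highest: x > 625

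**Where the scheme fails.**

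- High ends at 250 and Higher starts at 2U. They meet only if 2U = 250, so U = 125.
- If U > 125, no category covers 250 < x ≤ min(2U, 625). Higher becomes empty once 2U ≥ 625, so U ≥ 312.5.
- If U < 125, no value is lost, but values with 2U < x ≤ 250 meet Higher and also a lower category. The overlap reaches into Normal once 2U < 125, so U < 62.5.

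**Results.** Classifying values from 0.5 to 1000 pg/mL in steps of 0.5 under the literal rules gives the same ranges:

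| Assumed ULN | In no category | In two categories |
|---|---|---|
| 50 | none | above 100 to 250 (above 100 to 125 in Normal and Higher, the rest in High and Higher) |
| 100 | none | above 200 to 250 |
| 124 | none | above 248 to 250 |
| 125 | none | none |
| 126 | above 250 to 252 | none |
| 150 | above 250 to 300 | none |
| 200 | above 250 to 400 | none |
| 300 | above 250 to 600 | none |
| 312.5 or more | above 250 to 625 (Higher is empty) | none |

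**Likely origin.** The preceding shift definition, for ALT, ALP, AST and bilirubin, bounds Higher by 2 x ULN and 5 x ULN. The NT-proBNP line has the same structure with 125 in place of ULN everywhere except this one bound, which suggests a carry-over.

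**The case against.** The strongest reply is that this is an editorial slip whose meaning can be recovered. The categories are ordered, High stops at 2 x 125, and the treatment-emergent criteria use 2 x 125, so a careful programmer would start Higher there. The SAP also puts 125 where other analytes have ULN, which is compatible with 125 serving as the limit; in that case nothing changes numerically. All of this is fair. It supports the correction and keeps the point minor, but it does not make the written rule correct.

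A narrower objection is that the sentence tying ULN to the central laboratory concerns the predefined abnormality criteria and does not expressly cover the shift tables. That also stands: carrying it over is a reasonable inference, and the shift-table ULN is not separately defined.

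Three stronger readings are tempting, and the documents do not support them:

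- **That any ULN other than 125 leaves values unclassified.** This is true only above 125. Below 125 the fault is double classification.
- **That affected participants disappear from the safety reporting.** SAP 3.3 uses the number of observations as the shift-table denominator, so an unclassified value could show as cells that do not add up. A rise above 250 still meets the treatment-emergent criterion of more than 2 x 125. Section 4.6.3.2 also provides key subject information for treatment-emergent abnormalities, by-visit summaries and listings.
- **That NT-proBNP is the trial's designated marker of fluid overload.** The readable text lists it only as a safety laboratory test, and the monitoring items in the risk table are redacted.

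**Conclusion.** The definition is wrong as written. One of six NT-proBNP bounds uses ULN, and the categories form a proper partition only if that ULN is 125 pg/mL.

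The size cannot be fixed from the documents, because it depends on an unstated ULN and on how many participants have values in the affected range. It runs from nothing (ULN 125) to the whole band above 250 and up to 625 pg/mL unclassified (ULN 312.5 or more), with overlap instead of a gap when the ULN is below 125.

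Only one descriptive safety shift table is exposed. No key endpoint uses NT-proBNP, and the treatment-emergent counts, by-visit summaries and listings do not depend on the faulty bound. This is a minor correction, worth making before the tables are programmed.

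**What to change.** In SAP 4.6.3.1, change the lower bound of the NT-proBNP category Higher from more than 2 x ULN to more than 2 x 125. The categories become:

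- Normal: up to 125 pg/mL
- High: above 125 to 250
- Higher: above 250 to 625
- Highest: above 625

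Every value then falls in exactly one category whatever the laboratory range, and the cut-points agree with the treatment-emergent criteria in the same section. The cost is one term in the SAP and the matching line in the table specification. It needs no new data and no change to any other analysis.
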